Tobacco use is the leading preventable cause of morbidity and mortality in the United States (US) and Delaware,¹ claiming more than 400,000 US lives each year.² Tobacco use disorder (TUD), or the long-term problematic use of tobacco, has been recognized by the American Psychiatric Association as a substance use/behavioral health condition (see ³). The burdens of TUD disproportionately affect racial minorities and those with low socioeconomic status (SES), thereby contributing to tobacco-related health disparities (TRHDs).⁴ Underserved smokers are no less interested in quitting smoking and make just as many quit attempts as more advantaged smokers⁵ but are less likely to be advised to quit,⁶ have less access to treatment,⁷ use evidence-based treatments less frequently, report greater concerns about the safety of these medications, and ultimately experience lower abstinence rates.⁵ Hospital-based smoking cessation interventions have the potential to reach large segments of this underserved population. A Cochrane review found that hospital-based interventions significantly increase smoking cessation rates compared to usual care;⁸ however, rates rarely exceed 25%. Promising new evidence suggests that applying a *precision pharmacotherapy* approach based on the nicotine metabolite ratio (NMR), a commercially available, genetically-informed marker of nicotine metabolism rate can significantly improve cessation outcomes. Evidence from multiple independent studies,⁹⁻¹² including a recent randomized clinical trial (RCT),¹³ demonstrates that matching slow metabolizers of nicotine with the nicotine patch and fast metabolizers of nicotine with varenicline can maximize treatment response and minimize side effects. While encouraging, a critical gap in knowledge is how to best translate a precision pharmacotherapy approach into a hospital-based smoking cessation intervention and improve cessation rates for underserved smokers. Preliminary data suggest that personalized treatment recommendations may increase TUD medication uptake and effectiveness.^{14,15} Thus, the scientific premise of this application is that integrating a precision pharmacotherapy approach into a hospital-based TUD treatment program will increase medication uptake and effectiveness, with particular relevance for smokers from underserved communities.

2.0 STUDY POPULATION:

Approximately 100 adult current smokers (≥ 5 cigarettes/day), who are patients at the Helen F. Graham Cancer Center & Research Institute (Christiana Care) lung/thoracic clinic who are ages 18 and older. Exclusion criteria include: 1) use of non-cigarette tobacco products or current TUD treatment, 2) psychiatric or other medical contraindications to receiving TUD medication (assessed by the study physician), 3) no telephone, 4) medical instability, 7) inability to communicate in English, 8) unable to consent due to mental status, 9) estimated life expectancy of < 6 months, 10) pregnancy.

The duration of study participation will be approximately 6 weeks from the first through the final study visit.

3.0 STUDY PROCEDURES:

3.1 Overview of Proposed Research Design

This investigation employs a randomized controlled trial (RCT) study design. Participants will be randomized into either precision pharmacotherapy, where they will receive a personally-tailored recommendation for a TUD medication based on their NMR plus standard care, or to standard care only. Standard care will adhere to the Ask-Advise-Connect model where participants are asked about tobacco use, advised to quit smoking, offered a choice of FDA-approved TUD medication and offered a referral to the Delaware Quitline for access to counseling services and medications.

Upon enrollment into the study, the research assistant will verify demographic data, administer a baseline survey, and coordinate testing for the NMR at their in-person intake visit. Patients will be randomized to the precision or standard care arms in a 1:1 ratio. Following receipt of the NMR test results and randomization, the research assistant will follow-up with a pre-quit telephonic visit to review procedures with participants. For standard care, the research assistant will provide information on FDA-approved TUD medications and offer to coordinate the process of starting on a medication of the participants' choice (i.e., nicotine patch or varenicline), which participants can decline. Participants randomized to precision pharmacotherapy will be provided with their NMR result, information on how NMR impacts TUD treatment, and a personalized recommendation for medication based on their NMR result (i.e., varenicline for faster metabolizers, nicotine patch for slower metabolizers). Similar to standard care procedures, participants will be offered either the nicotine patch or varenicline and will not be required to choose the medication based on their personalized recommendation, or any medication. For participants in both conditions who opt for medication, per participant preference, medications can be prescribed by the study physician ([name]) or the patient can be referred to the Delaware Quitline for no-cost medications, a free service available to all Delaware residents. A 1-week follow-up telephonic visit will be conducted to collect data related to medication use, quit date or smoking rate, and side-effects. Finally, a 1-month follow-up in-person visit will be arranged to complete a follow-up survey and to assess smoking status.

3.2 Participant Identification and Recruitment

With the support of [name], thoracic surgeon, and lead for the "Lung Health Clinic" in the Helen F. Graham Cancer Center & Research Institute and [name], gynecologist and Director of the Division of Minimally Invasive Gynecologic Surgery at ChristianaCare, the research assistant will meet with prospective participants in the clinic or the Center for Advanced GYN & Minimally Invasive Surgery to screen for eligibility, discuss study

procedures, answer questions, and if appropriate review the consent and HIPPA forms. Patients will be clearly informed that not participating in this study will not preclude engaging in other smoking cessation programs, nor will accepting medication be a condition of participation.

Vulnerable Populations: Pregnant women and fetuses, children, neonates, and prisoners are not included in this research study. Women who are pregnant at the time of the baseline assessments will not be eligible for the study. Women will be advised to notify the study staff if they become or intend to become pregnant during the study period.

Populations vulnerable to undue influence or coercion: Educationally or economically disadvantaged persons are included but not solely targeted for recruitment. Cognitively impaired persons, including those with poorly managed serious psychiatric conditions, are not included in the current study.

The study consent includes language that informs participants that their care will not be affected if they choose not to participate in the study or withdraw after enrollment. The Principal Investigator may withdraw participants who violate the study plan, to protect the participant for reasons related to safety, or for administrative reasons. Whether or not each participant completes the study will be tracked.

3.3 Study Procedures & Data Collection

The following study procedures will be implemented. A description of the measures used to collect data during these procedures is provided below.

- **Intake Session (completed during clinic visit)**
 - Participants will complete a self-report survey of demographics, smoking history, and beliefs about the use of smoking cessation aids.
 - **[Women only]** A pregnancy screen will be administered for women capable of becoming pregnant (55 and under). NOTE: For safety reasons, pregnant women will not be eligible to participate in the research study.
 - The research assistant will complete the blood draw to be used for a nicotine metabolite ratio (NMR) test and arrange for the sample to be transported to the laboratory for processing.
- **Randomization:** Following completion of the 'intake session' and receipt of NMR testing results, participants will be randomized in a 1:1 ratio to either of the following conditions:
 - **Treatment Plan Option 1 (Standard Care):** Standard smoking cessation counseling will be offered + participant choice of nicotine patches or varenicline. Participants are also free to decline either medication.
 - **Treatment Plan Option 2 (Precision Pharmacotherapy):** Standard smoking cessation counseling will be offered + a recommendation to take either the nicotine patch or varenicline based on the results of the NMR test. Regardless of the recommendation, it would still remain the participant's choice to be prescribed either nicotine patches or varenicline. Participants are also free to decline either medication.
- **Pre-Quit Telephonic Visit:** This visit will take place after the NMR results have been received and randomization is complete, approximately 7-14 days following the intake session (depending on lab processing time).

- Participants will be informed of their treatment condition, including the recommended medication if assigned to 'treatment plan option 2' (i.e., the precision pharmacotherapy arm).
- Participants will be offered their choice of either the nicotine patch or varenicline. Participants will be reminded that taking medication is not a condition of participation in the study. In addition, participants assigned to 'treatment plan option 2' (i.e., the precision pharmacotherapy arm) will not be required to accept only the medication recommended to them based on the results of NMR testing.
- For participants who elect to take a medication, the research assistant will communicate with the study physician ([name]), or the investigators at the Center for Advanced GYN & Minimally Invasive ([name] or [name]) to arrange for a prescription and/or referral to the Delaware Quitline, per participant preference.
- Even for participants who receive a prescription in the clinic or at the Center for Advanced GYN & Minimally Invasive Surgery, a referral to speak with a smoking cessation counselor, which is made available at no-cost to all Delaware residents through the Delaware Quitline.
- Follow-up Telephonic Visit:** This session will occur one week after the pre-quit telephonic/virtual visit.
 - Participants will answer brief questions regarding medication use, quit date or smoking rate if still smoking, and side effects.
- In-Person Assessment:** This session will occur four weeks after the pre-quit telephonic/virtual visit. The research assistant will arrange to meet participants at the clinic.
 - Participants will again complete a brief assessment of medication use, quit date or smoking rate if still smoking, and side effects.
 - Participants who self-report smoking cessation will complete a carbon monoxide (CO) reading by breathing into a machine provide a biochemical confirmation of smoking status.

The measures referenced above will be administered accordingly:

Study Measure	Intake Session Enrollment (in-person)	Pre-Quit Visit Week 0 (phone)	Follow-Up Visit Week 1 (phone)	Final Assessment Week 4 (in-person)
Demographics	X			
Smoking History	X			
NMR	X			
Medication use, quit date or smoking rate, side-effects			X	X
Carbon Monoxide reading				X

- **Demographics.** The research assistant will confirm demographic data collected from the EHR and collect additional characteristics, including address, phone number, date of birth, race/ethnicity, employment status, education level, and income.
- **Smoking history.** Participants will be asked standard questions about cigarette use, including the number of cigarettes smoked per day, the age of smoking onset, whether the participant ever quit smoking previously and for how long, and whether the participant ever utilized smoking cessation aids previously. In addition, participants will be administered the first item from the Fagerström Test for Nicotine Dependence (FTND), a measure of nicotine tolerance and withdrawal.¹⁷
- **Nicotine Metabolite Ratio (NMR).** NMR testing for cotinine and 3-hydroxycotinine following standard procedures at a commercial laboratory contracted with ChristianaCare (i.e., Quest).¹⁹
- **Medication use quit date or smoking rate, and side effects.** At the follow-up call and in-person assessment, the research assistant will use the timeline follow-back interview method²⁰ to ask participants whether they quit smoking (including the quit date). If participants did not successfully quit smoking, current rates of smoking will be assessed. In addition, the research assistant will ask about medication usage and side-effects.
- **Carbon monoxide reading.** For participants self-reporting smoking cessation, biochemical verification of smoking status will be conducted with the use of a breath carbon monoxide monitor manufactured by Vitalograph according to standard procedures.²¹

4.0 RISKS AND BENEFITS TO PARTICIPANTS:

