Exploratory Aim: *Precision pharmacotherapy will improve patient outcome expectancies related to medication effectiveness and safety/side effects, which will be associated with greater use of pharmacotherapy (H3.1) and abstinence (H3.2). Higher rates of treatment matching in precision care will mitigate the reductions in abstinence rates for low-SES/racial minority smokers compared to standard care (H3.3).*

Mediation analyses. Two sets of logistic regression models will be used to evaluate whether patient outcome expectancies mediate the relationship between treatment assignment (precision vs. standard) and the outcome measures use of pharmacotherapy and abstinence. In the first step for each model, treatment condition will be used to predict the outcome measures, adjusting for the same covariates used above. In the second step, patient outcome expectancies will be used to predict the outcome measures, again adjusting for covariates. If both treatment condition and treatment expectancies are significantly associated with outcome measures, a third step will include both predictors to formally test for partial or complete mediation by assessing whether the inclusion of patient outcome expectancies reduces or eliminates the effect for treatment assignment.

Moderation analyses. A series of logistic regression models will be used to evaluate whether greater treatment matching mitigates (i.e., moderates) the lower rates of abstinence typically seen among low-SES/racial minority patients in usual care. The model will include the predictors of treatment matching (dummy coded as yes/no based on whether the participant used the medication matched to their nicotine metabolism rate: NRT for slower metabolizers, varenicline for faster metabolizers), measures of SES (e.g., years of education), and the product of these predictors. If the product, or interaction term, significantly predicts abstinence, that would provide evidence that treatment matching has differential impacts based on the SES of the participant. Post hoc analyses will be employed to describe the nature of the interaction. A

similar, albeit multilevel approach will be used to test for interaction between area-level variables (e.g., census tract poverty levels, tobacco outlet density) and treatment matching.

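### H3.1 and H3.2: the mediation plan never models expectancies on treatment, has no defined criterion for mediation, and does not say which visit supplies the mediator

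*Protocol*

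**What the plan says.** The Exploratory Aim in the SAP sets out a causal chain. Its first link is "Precision pharmacotherapy will improve patient outcome expectancies related to medication effectiveness and safety/side effects". The expectancies are then tied to use of medication (H3.1) and to abstinence (H3.2).

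Under Mediation analyses, the first step regresses each outcome on treatment and the second regresses it on expectancies, both with covariates. Then: "If both treatment condition and treatment expectancies are significantly associated with outcome measures, a third step will include both predictors". Mediation is judged by "assessing whether the inclusion of patient outcome expectancies reduces or eliminates the effect for treatment assignment". The SAP names neither an instrument nor a visit for the expectancy score.

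The Protocol fixes the order of events:

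- **Intake (3.3).** "Participants will complete a self-report survey of demographics, smoking history, and beliefs about the use of smoking cessation aids".
- **Randomisation (3.3).** "Following completion of the 'intake session' and receipt of NMR testing results, participants will be randomized in a 1:1 ratio".
- **Pre-quit call (3.1 and 3.3).** After randomisation "the research assistant will follow-up with a pre-quit telephonic visit to review procedures with participants". At this call, about 7 to 14 days after intake, participants learn their assignment and are offered medication.
- **Weeks 1 and 4 (3.3).** The listed content is medication use, quitting or smoking rate, and side effects, with a carbon monoxide reading at week 4. Beliefs are not listed.
- **One month (3.1).** A follow-up survey is mentioned, but its content is not given.

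Section 3.3 also promises that "A description of the measures used to collect data during these procedures is provided below", and introduces its table with "The measures referenced above will be administered accordingly". Neither the descriptions nor the table mentions beliefs or expectancies.

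**The concern.** A mediator has to be something that treatment can change, and the claim needs two links: treatment to expectancies, and expectancies to outcome. The SAP examines the second link and the total effect. The first link is asserted in the hypothesis but has no model of its own, so a report could claim mediation without showing that precision care changed expectancies at all.

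The criterion adds to the problem. The SAP does not say how much the treatment coefficient must fall to count as reduced, and it asks for no estimate of the indirect effect and no interval. Two analysts could reach opposite conclusions from the same output.

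The unnamed visit decides what the result can mean. An intake score cannot respond to assignment. A week 4 score can, but it comes after the medication choice that H3.1 seeks to explain and at the same visit as the abstinence assessment that H3.2 seeks to explain. Quitting, or experience with the medication, could then alter expectancies rather than the reverse.

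**Working it through.** The documents give no power or effect size for this aim, so there is no figure of the plan's own to reproduce. The main check is a reading of the steps; the simulations only illustrate size.

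**1. Which links the SAP models.** Let a be the effect of treatment on expectancies and b the effect of expectancies on outcome given treatment. On a linear scale the indirect effect is a × b.

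| SAP step | Model | Link addressed |
|---|---|---|
| 1 | outcome on treatment | total effect |
| 2 | outcome on expectancies | outcome link, treatment not included |
| 3 | outcome on both | b, and the remaining treatment effect |
| none | expectancies on treatment | a |

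**2. If the intake score is the mediator.** It is fixed before randomisation, so a = 0 and a × b = 0 whatever b is. Chance imbalance remains. With about 100 participants allocated 1:1 there are about 50 per arm, and the standardised arm difference has SD √(2/50) = 0.20. That is enough to move the treatment coefficient in step 3 by chance.

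**3. How often the SAP steps report mediation when there is none.** Settings: n = 100, 1:1, two-sided 5% at steps 1 and 2, complete follow-up, SAP covariates omitted. All inputs are assumed except one baseline rate: the Protocol introduction says hospital-based cessation rates rarely exceed 25%, and ln(0.25/0.75) = −1.10. A 50% rate (intercept 0) was also used. The arm log-odds ratio was 0.5, 0.9 or 1.2, none of it passing through expectancies.

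- *Intake score:* standard normal, independent of arm, log-odds 0.3, 0.6 or 1.0 per SD on the outcome.
- *Week 4 score:* 0.5 × intake + √0.75 × noise + r × abstinent, with r = 0.3, 0.5 or 0.8 SD. Quitting raises the score; the score has no effect on quitting.

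| Score used | Any shrinkage counts | At least 10% shrinkage, or loss of significance, required |
|---|---|---|
| Intake | about 2% to 14% | under 5% |
| Week 4 | about 3% to 41% | about 1% to 16% |

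The percentages are of all simulated trials. Separate runs agreed within simulation error.

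**4. Whether a better test repairs week 4 timing.** Requiring both a and b to be significant in the same week 4 scenario still reports mediation in 2% to 3%, 4% to 8% and 7% to 21% of trials for r = 0.3, 0.5 and 0.8. It helps, but it cannot settle the direction of effect.

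**5. Precision of the missing first link.** The smallest arm difference in expectancies detectable with 80% power, unadjusted, is (1.96 + 0.84) × √(2/50) = 2.80 × 0.20 = 0.56 SD. Power for assumed differences of 0.3, 0.4, 0.5 and 0.6 SD is about 32%, 52%, 71% and 85%.

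**The case against.** A reader might infer that expectancies are measured only before randomisation and that the mediation analysis is therefore void. The documents do not support that, for three reasons:

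- Protocol 3.1 pairs a baseline survey with a 1-month follow-up survey, which may repeat the belief items.
- The measures table is weak evidence to the contrary. It has no row for the beliefs that are collected at intake, nor for the pregnancy screen, so its silence about week 4 shows little.
- The intake item concerns beliefs about cessation aids, while the SAP's mediator is expectancies about effectiveness and safety. The documents do not say that these are the same measure.

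A reader might also infer that the SAP steps often produce false mediation. With an intake score, that depends on counting any fall in the coefficient, however small. Under either stricter reading the rate stays below 5% in every setting tried. The week 4 figures hold up only in part, mainly when quitting shifts the score by 0.5 to 0.8 SD. The stricter thresholds are themselves assumptions, so the fair criticism is that the SAP leaves the criterion undefined.

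Finally, in a linear model the fall in the treatment coefficient equals a × b, so the shrinkage rule reflects the first link indirectly. That is fair. It does not supply a test or interval for that link, and the SAP's models are logistic.

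What stands after these objections is the absence of a treatment-on-expectancies model, the undefined criterion, and the unnamed instrument and visit.

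**Conclusion.** The point holds as a minor finding. That the first link of H3.1 and H3.2 is never modelled follows from reading the SAP's steps and needs no assumption about timing. Timing determines what can be claimed: with an intake score, no mediation is possible; with a week 4 score, the analysis is meaningful but can show only an association.

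The simulated rates rest on assumed effects, complete follow-up and no covariates, and they vary widely with how a reduction is defined. They show that the rule is loose; they do not estimate this trial's error rate.

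Only two exploratory hypotheses of a pilot are affected. Specific Aims 1 and 2 and H3.3 do not use the expectancy measure.

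**What to change.** In the SAP:

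1. Name the expectancy instrument and the visit whose score is the mediator. That visit must follow disclosure of assignment.
2. Add a model of that score on treatment, adjusted for the same measure at intake if it was collected.
3. Replace the coefficient-shrinkage rule with an indirect-effect estimate and 95% confidence interval (bootstrap, for example), and state the assumption of no unmeasured mediator-outcome confounding.
4. If the score comes from week 4, say that temporal order is not established and describe the result as an association.
5. If no post-assignment score is collected, withdraw the mediation claim and use intake beliefs only as a baseline predictor or moderator.

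If week 4 is the source, the Protocol also needs a description of the measure and a row in the 3.3 table. Otherwise the change is to SAP text alone. The cost is a little more analysis work, and the interval will be imprecise at about 50 per arm, which the report should say.

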Document: Statistical Analysis Plan

Document Date: March 5, 2020

Official Study Title: A Pilot Pragmatic RCT of a Hospital-based Precision Pharmacotherapy Smoking Cessation Program

NCT#: NCT04897607

Statistical Analysis Plan

Specific Aim 1: *The proposed trial will be acceptable to underserved smokers as measured by the proportions and demographic characteristics of patients who enroll (H1.1), accept pharmacotherapy (H1.2), and complete follow-up (H1.3).*

Descriptive statistics and 95% confidence intervals will be used to summarize the feasibility metrics, namely the numbers and proportions of patients who: 1) were approached, 2) deemed eligible, 3) enrolled, 4) accepted pharmacotherapy, and 5) completed follow-up. To gain a sense of whether study participants may be considered representative of the larger population of ChristianaCare smokers as measured by race and area-level measures of SES, chi-square tests and Wilcoxon rank tests will be conducted. Race is routinely collected for all admitted patients and will permit a comparison between trial participants and the larger population of ChristianaCare smokers. However, no individual-level measures of SES are routinely collected for admitted patients and therefore will not allow for a comparison between trial participants and the larger population. Therefore, census tract measures of poverty (e.g. employment status, income, and education) based on participant residence will be used as a proxy for individual-level SES. The residential addresses for the larger population of ChristianaCare smokers has been previously geocoded and linked to census tract poverty measures,⁴⁸ which will be used to compare the proportions of participants in this trial who reside in each census tract strata.

Specific Aim 2: *Patients assigned to precision care will more readily accept pharmacotherapy (H2.1), achieve greater treatment matching (H2.2), and demonstrate improved abstinence rates (H2.3).*

Three sets of logistic regression models will be used to compare precision pharmacotherapy vs. standard care for each of the binary effectiveness outcome measures: acceptance of pharmacotherapy, treatment matching, and abstinence. Models will adjust for demographics and other covariates, including age, race/ethnicity, nicotine dependence, and indicators of SES (employment status, income, and education).

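### Allocation follows the NMR result, but no stratification or adjustment by metabolizer group is specified: a cheap, modest gain in balance and precision is left unused

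*Protocol*

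**What the plan says.** Protocol section 3.1 gives the allocation as "Patients will be randomized to the precision or standard care arms in a 1:1 ratio". Section 3.3 adds the timing: "Following completion of the 'intake session' and receipt of NMR testing results, participants will be randomized in a 1:1 ratio". Neither document names a stratification factor, a block scheme, minimisation or a way of generating the sequence. The planned size, in section 2.0, is "Approximately 100 adult current smokers", so about 50 per arm.

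Metabolizer group has two roles after allocation:

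- **Recommendation.** In the precision arm the drug is recommended by group: "varenicline for faster metabolizers, nicotine patch for slower metabolizers" (Protocol section 3.1).
- **Outcome definition.** The SAP, under the moderation analyses of the Exploratory Aim, codes matching by whether the participant "used the medication matched to their nicotine metabolism rate: NRT for slower metabolizers, varenicline for faster metabolizers".

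Under Specific Aim 2 the SAP compares the arms on three binary outcomes: "acceptance of pharmacotherapy, treatment matching, and abstinence". The models adjust for demographics and other covariates, "including age, race/ethnicity, nicotine dependence, and indicators of SES (employment status, income, and education". Metabolizer group is not in that list. Neither document gives the NMR cut-off that separates slower from faster metabolizers, or the expected share of each.

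**The concern.** Metabolizer group is the baseline variable closest to the trial's hypothesis, and under section 3.3 it is known before allocation. Matching is defined by it, so the match rate expected in standard care depends on the mix of slower and faster metabolizers who fall into that arm. The background section of the protocol also rests on the two groups responding differently to the two drugs, so the mix may bear on abstinence as well.

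In a trial of about 100, a chance difference in that mix is not rare, and neither the stated design nor the named covariates deal with it. At stake is the reading of H2.2 (matching) and, to an extent that cannot be worked out from the documents, H2.3 (abstinence).

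A related gap concerns the label itself. In the precision arm a slower/faster label must exist in order to make the recommendation. In standard care no described step needs one until matching is coded, which may be after drug choice is known.

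**Working it through.** The documents give no figure on this point to reproduce.

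**Inputs from the documents:** N about 100; 1:1 allocation, so 50 per arm; matching defined by metabolizer group. I assume the definition in the moderation section also applies to H2.2.

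**Assumptions, because the documents are silent:** 25%, 40% or 50% of participants are slower metabolizers; 70% of standard-care participants accept medication; 70-80% of acceptors choose the same drug, independently of metabolizer group.

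**Step 1: how often the arms differ.** Let K of 100 participants be slower. With a fixed 50/50 split, the number X in one arm is hypergeometric (100, K, 50), and the between-arm gap in slower share is |X - (K - X)| / 50.

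| Slower in sample (K) | P(gap ≥ 10 points) | P(gap ≥ 16 points) | P(gap ≥ 20 points) |
|---|---|---|---|
| 25 | 0.356 | 0.063 | 0.020 |
| 40 | 0.307 | 0.153 | 0.066 |
| 50 | 0.317 | 0.161 | 0.071 |

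Gaps move in steps of 4 points, so for K = 40 or 50 a gap of at least 10 points means at least 12.

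The result does not depend on the unstated method. Simulation with the number of slower metabolizers also varying gives P(gap ≥ 10 points) of 26-33% under coin-flip allocation and 30-37% under an unstratified fixed 50:50 split. The standard deviation of the gap, sqrt(4p(1-p)/N) with p the slower share, is sqrt(4 × 0.25 × 0.75 / 100) = 8.7 points at p = 0.25 and 10.0 points at p = 0.50.

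**Step 2: what a gap does to the standard-care match rate.** Let s be the slower share in the standard arm, a the acceptance and v the share of acceptors choosing the drug matched to faster metabolizers. Then

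match rate = a × [s(1 - v) + (1 - s)v],

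so a change Δs moves it by Δs × a × |2v - 1|. (If the favoured drug is the other one, the size is the same.) With a = 0.70, the multiplier is 0.70 × 0.40 = 0.28 at v = 0.70 and 0.70 × 0.60 = 0.42 at v = 0.80.

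With equal arms, a between-arm gap of G moves each arm by G/2 from the sample share:

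- G = 10 points: Δs = 5 points, shift = 5 × 0.28 to 5 × 0.42 = **1.4 to 2.1 points**.
- G = 20 points: Δs = 10 points, shift = **2.8 to 4.2 points**.

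The arm difference moves by more than this only if match rates in the precision arm also differ between the two metabolizer groups in the same direction. The documents give no basis for a figure there.

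**Step 3: scale.** With match rates of, say, 35% and 50% (assumed), the standard error of the arm difference is sqrt(0.35 × 0.65 / 50 + 0.50 × 0.50 / 50) = 9.8 points. A shift of 1.4-2.1 points is 0.14-0.21 of that.

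**Step 4: with stratification.** Permuted blocks of 4 or 6 within metabolizer group (N = 100, simulated) reduce the standard deviation of the gap to 1.3-1.7 points. The largest gap seen was about 4 points with blocks of 4 and 6 points with blocks of 6. No run reached 10 points.

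**The case against.** The strongest reply is that unstratified 1:1 allocation is valid. Chance imbalance is already part of the standard error and does not bias the test. A shift of about a fifth of a standard error or less matters little in a pilot whose first aim is acceptability and which makes no power claim. All of this stands, and it limits the point to an inexpensive improvement.

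Four stronger readings are tempting, and the documents do not support them:

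- **That the plan uses simple randomisation.** It states only the ratio and timing. What can be said is that no stratification by metabolizer group is specified.
- **That participants are held 7-14 days for a result that is then unused.** Section 3.3 gives 7-14 days as the timing of the pre-quit call, dependent on laboratory processing. The precision arm needs the result for its recommendation, and the same wait in both arms keeps visit timing alike.
- **That the analysis rules out adjustment.** The SAP's covariate list is introduced as an inclusion, so it is open. Metabolizer group is unnamed, not excluded.
- **That a shift of 2.8-4.2 points occurs in about a third of trials.** The 31-36% belongs to a between-arm gap of at least 10 points. A standard-care shift of 2.8-4.2 points needs a gap of 20.

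It is also fair to say that the integrity of the label depends mainly on fixing the cut-off in advance. A pre-specified cut-off would secure the label with or without strata.

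**Conclusion.** The point holds as a modest one, for consideration. A variable that sets the recommendation and defines an Aim 2 outcome is available at allocation, and no stated part of the design or analysis balances it or adjusts for it. A between-arm gap of 10 points or more would arise in about a third of such trials, yet at 10 points it moves the standard-care match rate by only about 1.4-2.1 points. The larger shift of 2.8-4.2 points belongs to a 20-point gap, reached or exceeded in 2-7% of trials. These sizes rest on the assumed slower share, acceptance and drug preference. The effect on abstinence cannot be quantified from the documents. A reader might infer that the matching or abstinence comparison is biased. It is not: the cost is some precision and the risk that one small trial's estimate is distorted by an unlucky split.

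**What to change.** In Protocol section 3.3, under Randomization:

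- Fix the NMR cut-off used for the recommendation before the first allocation.
- Record each participant's slower/faster label, in both arms, before allocation.
- Randomise 1:1 in concealed permuted blocks of varying size within the two metabolizer strata.

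In the SAP:

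- Code treatment matching in both arms from the stored label.
- Name metabolizer group as a covariate in the Aim 2 models.

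The cost is two allocation lists instead of one, and a cut-off settled in advance, which the recommendation needs in any case. No visit, sample or delay is added, since the result is already awaited. If the allocation scheme can no longer be changed, the pre-specified cut-off, the stored label and the added covariate are still worthwhile. The covariate would then deal with chance imbalance at the analysis stage.
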